#### **9.4 *Withdrawal of Participants***

A participant should be withdrawn from the study if any of the following occur:

- 1) Withdrawal of participant consent.
- 2) Investigator determines that withdrawal from the study is in the best interest of the participant.
- 3) Major protocol violation (i.e., circumstances where confounding conditions make it impossible to derive sound scientific or medical conclusions from the primary endpoint data generated on a participant).
- 4) Any condition, injury, or disease that becomes apparent during the study and necessitates the termination of the participant from the study; including events detailed in Section 7.3.1 - Safety Stopping Rules.
- 5) Administrative reason (e.g., termination of the clinical study by a Regulatory Agency or the Sponsor).

#### **9.5 *Participant Withdrawal Procedures***

##### **9.5.1 *Follow-up Procedures for Participants Who Withdraw Prematurely***

The date and the reason for study drug discontinuation or participant withdrawal from the study must be recorded on the Case Report Form. Participants who prematurely discontinue the study for any reason will be asked to attend the final/ early discontinuation visit but are not required to attend a follow up visit unless deemed necessary at the discretion of the investigator.

##### **9.6 *Procedures for Replacing Participants Who Withdraw***

Should any participant withdraw from the study prior to study completion, leading to insufficient or uninformative data for analysis, the participant may be replaced, at the sponsor's discretion. If a participant is replaced, instructions in Section 7.5 will be followed for randomization and assignment of a study number.

## 10 TREATMENT PLAN AND METHODS

### 10.1 Schedules of Assessments – Primary and Extension

**Table 1 - Schedule of Assessments – Primary Study Only**

Visit Name and Number	V1				V2 Baseline V2	V3	Blood draw only	V4	V5	V6	V7	V8	V9	V10	Final/ Early Discontinuation V11	V12
	Step 1	Step 2	Step 3	Step 4												
Study Day		-60 to -1			1	15 (+/-2)	21 (+/-1)	29 (+/-2)	43 (+/-2)	64 (+/-2)	85 (+/-7)	106 (+/-2)	127 (+/-2)	148 (+/-2)	169 (+/-7)	183 (+/-2) from V11)
Informed consent capability	X															
Written informed consent 	X															
Demographic information	X															
General medical, surgical and psychiatric history	X															
Inclusion/exclusion criteria	X	X		X												
Modified Hachinski	X															
Geriatric Depression Score	X															
C-SSRS	X				X	X		X	X	X	X	X	X	X		
Diagnosis of Probable AD 	X															
 F-FDG Imaging															X	
 C -UCB-J Imaging (SV2A imaging)														X		
Amyloid imaging (e.g.  C - PIB Imaging) 			X													
MR Imaging (Safety MRI, resting state BOLD)		X									X				X	
MMSE	X								X		X		X		X	
ADAS-Cog 14, NTB 					X				X		X		X		X	
CDR-SB 					X				X		X		X		X	

Visit Name and Number	V1				Baseline V2	V3	Blood draw only	V4	V5	V6	V7	V8	V9	V10	Final/ Early Discontinuation V11	V12
	Step 1	Step 2	Step 3	Step 4												
Study Day	-60 to -1				1	15 (+/-2)	21 (+/-1)	29 (+/-2)	43 (+/-2)	64 (+/-2)	85 (+/-7)	106 (+/-2)	127 (+/-2)	148 (+/-2)	169 (+/-7)	183 (14 D (+/-2) from V11)
ADCS-CGIC 					X			X			X		X		X	
ADCS-ADL 					X			X			X		X		X	
Physical Examination	X				X	X	X	X	X	X	X	X	X	X	X	X
ECG	X				X		X				X	X			X	X
Vital signs, weight 	X				X	X	X	X	X	X	X	X	X	X	X	X
Hematology, biochemistry	X				X	X	X	X	X	X	X	X	X	X	X	X
Urinalysis	X				X	X	X	X	X	X	X	X	X	X	X	X
Coagulation 	X													X		
Serology: Syphilis, HIV, HepB, HepC 	X															
Thyroid panel (T3, T4, TSH), B12, folate 	X															
APOE status	X															
CSF sampling for PK and PD 				X											X	
Plasma sampling for PK 					X	X	X	X	X	X	X	X	X	X	X	X
Dispense study drug 					X						X					
Drug return and drug accountability						X		X	X	X	X	X	X	X	X	X
Recording concomitant medication	X				X	X	X	X	X	X	X	X	X	X	X	X
Recording of adverse events 		X		X	X	X	X	X	X	X	X	X	X	X	X	X

Key for Schedule of Assessments

1. Informed consent must be obtained prior to the participant undergoing any study-specific procedures.
2. Confirm AD diagnosis (NIA-AA 2011 criteria, McKhann et al, 2011)].
3. Perform brain amyloid imaging (PET scan). Amyloid imaging of the brain may not be required if there is evidence of positive Alzheimer's disease biomarkers based on amyloid PET imaging or CSF A $\beta$ .
4. Cognitive testing will include the ADAS-Cog 14 and NTB. Cognitive assessments will be locally administered by trained site staff and then centrally scored by a qualified central reviewer. Sites will be provided with copies of the scored assessments for their own records.
5. Functional testing will include CDR-SB, ADCS-CGIC and ADCS-ADL
6. Vital signs will include body temperature, seated systolic and diastolic BP, pulse rate and respiratory rate (Section 15.1.5).
7. Coagulation panel may be repeated upon admission as medically indicated or required by local practice.
8. Serology for hepatitis B (HbsAg), hepatitis C (HCV) and HIV (Section 14.2).
9. Clinical laboratory testing (Section 14).
10. Height will be recorded only at screening; Weight will be collected at every visit. (Section 15.1.3).
11. During Screening (post-consent), only SAEs related to a study-specific procedure will be collected. For all related AEs of moderate or severe intensity ongoing at the end of the study, follow-up will continue until the event has resolved to baseline severity, the event is assessed as stable by the Investigator, or the patient is lost to follow-up or the patient withdraws consent.
12. CSF Sampling: (see Section 11).
13. Blood collection (see Section 14).
14. On clinic visit dates, subject should hold dose in AM and dosing should occur in the clinic.

**Table 2 - Schedule of Assessments –Primary and Extension Study**

Visit Name and Number	V1				Baseline V2	V3	Blood draw only	V4	V5	V6	V7	V8	V9	V10	V11	V12 E	V13	V14	Final / Early Discontinuation V15	V16
	Step 1	Step 2	Step 3	Step 4																
Study Day	-60 to -1				1	15 (+/-2)	21 (+/-1)	29 (+/-2)	43 (+/-2)	64 (+/-2)	85 (+/-7)	106 (+/-2)	127 (+/-2)	148 (+/-2)	169 (+/-7)	211 (+/-3)	253 (+/-3)	295 (+/-3)	337 (+/-7)	351 (14 D (+/-2) from V15)
Informed consent capability	x																			
Written informed consent 	x																			
Demographic information	x																			
General medical, surgical and psychiatric history	x																			
Inclusion/exclusion criteria	x	x		x																
Modified Hachinski	x																			
Geriatric Depression Score	x																			
C-SSRS	x					x														
Diagnosis of Probable AD 	x																			
 F-FDG Imaging																				
 C -UCB-J Imaging (SV2A imaging)																				
Amyloid imaging (e.g.  C -PiB Imaging) 																				
MR Imaging (Safety MRI, resting state BOLD)		x																		
MMSE	x																			
ADAS-Cog 14, NTB 																				

Visit Name and Number	V1				Baseline V2	V3	Blood draw only	V4	V5	V6	V7	V8	V9	V10	V11	V12 E	V13	V14	Final / Early Discontinuation V15	V16
	Step 1	Step 2	Step 3	Step 4																
Study Day	-60 to -1				1	15 (+/-2)	21 (+/-1)	29 (+/-2)	43 (+/-2)	64 (+/-2)	85 (+/-7)	106 (+/-2)	127 (+/-2)	148 (+/-2)	169 (+/-7)	211 (+/-3)	253 (+/-3)	295 (+/-3)	337 (+/-7)	351 (14 D (+/-2) from V15)
CDR-SB 					X			X			X		X		X		X		X	
ADCS-CGIC 					X			X			X		X		X		X		X	
ADCS-ADL 					X			X			X		X		X		X		X	
Physical Examination	X				X	X	X	X	X	X	X	X	X	X	X	X	X	X	X	X
ECG	X				X		X				X				X				X	
Vital signs, weight  , 10	X				X	X	X	X	X	X	X	X	X	X	X	X	X	X	X	X
Hematology, biochemistry	X				X	X	X	X	X	X	X	X	X	X	X	X	X	X	X	X
Urinalysis	X				X	X	X	X	X	X	X	X	X	X	X	X	X	X	X	X
Coagulation 	X													X						
Serology: Syphilis, HIV, HepB, HepC 	X														X					
Thyroid panel (T3, T4, TSH), B12, folate 	X																			
APOE status	X																			
CSF sampling for PK and PD 															X					X
Plasma sampling for PK 					X	X	X	X	X	X	X	X	X	X			X	X	X	X
Dispense study drug 					X						X				X		X			
Drug return and drug accountability						X		X	X	X	X	X	X	X	X	X	X	X	X	X
Recording concomitant medication	X				X	X	X	X	X	X	X	X	X	X	X	X	X	X	X	X
Recording of adverse events 		X	X	X	X	X	X	X	X	X	X	X	X	X	X	X	X	X	X	X

Key for Schedule of Assessments

1. Informed consent must be obtained prior to the participant undergoing any study-specific procedures.
2. Confirm AD diagnosis (NIA-AA 2011 criteria, McKhann et al, 2011)].
3. Perform brain amyloid imaging (PET scan). Amyloid imaging of the brain may not be required if there is evidence of positive Alzheimer's disease biomarkers based on amyloid PET imaging or CSF A $\beta$ .
4. Cognitive testing will include the ADAS-Cog 14 and NTB. Cognitive assessments will be locally administered by trained site staff and then centrally scored by a qualified central reviewer. Sites will be provided with copies of the scored assessments for their own records.
5. Functional testing will include CDR-SB, ADCS-CGIC and ADCS-ADL
6. Vital signs will include body temperature, seated systolic and diastolic BP, pulse rate and respiratory rate (Section 15.1.5).
7. Coagulation panel may be repeated upon admission as medically indicated or required by local practice.
8. Serology for hepatitis B (HbsAg), hepatitis C (HCV) and HIV (Section 14.2).
9. Clinical laboratory testing (Section 14).
10. Height will be recorded only at screening. Weight will be collected at every visit. (Section 15.1.3).
11. During Screening (post-consent), only SAEs related to a study-specific procedure will be collected. For all related AEs of moderate or severe intensity ongoing at the end of the study, follow-up will continue until the event has resolved to baseline severity, the event is assessed as stable by the Investigator, or the patient is lost to follow-up or the patient withdraws consent.
12. CSF Sampling: (see Section 11).
13. Blood collection (see Section 14).
14. On clinic visit dates, subject should hold dose in AM and dosing should occur in the clinic.
15. The Visit 15 lumbar puncture and collection of CSF samples for PK and PD analyses is optional.

## **10.2 Study Specific Procedures**

### **10.2.1 Screening Visit 1, Steps 1-4**

Screening assessments may be performed during multiple visits over a period of 60 days prior to dosing with the determination of inclusion and exclusion criteria occurring over Visits V1 through V1.3. If needed for biomarker collection or interpretation or for logistical reasons, this period can be prolonged with written approval from the Sponsor. Steps 3 and 4 assessments may only be performed after completion of Steps 1 and 2 assessments which are necessary for determination of eligibility for continued participation. The order of individual assessments within a step is not fixed, unless indicated otherwise. Different screening assessments associated with each step may be performed on a single visit day or spread over multiple visits days. Eligible participants based on Steps 1 to 4 assessments will return to the site to have Baseline/ Visit 2. Although visit numbers are specified, fewer or additional visits can occur based on the above, and the numbering is considered guidance.

The following procedures will be performed as part of the Step 1/ Screening visit/s:

- Determine informed consent capability
- Obtain signed Informed Consent Form from participant
- Evaluate participant eligibility against study inclusion/exclusion criteria including administration of the Mini-Mental State Exam (MMSE), Geriatric Depression Scale (GDS) and modified Hachinski scale. (See section 16 for details)
- Record demographic information and confirm ethnicity
- Perform complete physical examination (see Section 15.1.3 for details)
- Medical, surgical and psychiatric history (see Section 15.1.4 for details)
- Measure and record vital signs and weight (see Section 15.1.5 for details)
- Confirm diagnosis of Probable AD according to 2011 NIA-AA criteria
- Perform 12-lead ECG (see Section 15.1.6 for details)
- Draw blood and prepare samples for ApoE status. Apolipoprotein E (ApoE) genotype is associated with the risk and age of onset of AD. Blood samples (approximately 10 mL) to perform this testing will be collected and will be utilized to further understanding of response to CT1812. The genotyping is mandatory for participation in the study

and the results will not be revealed to either the participant or caregiver or study partner.

- Draw blood and prepare samples for serum chemistry, hematology, viral serology, thyroid panel and coagulation panel (see Section 14 for details). Abnormal results at screening will exclude a participant unless the investigator is aware of a specific reason that can explain the abnormality (e.g., elevated creatine phosphokinase [CPK] 24 hours after strenuous exercise). Should an abnormal lab remain abnormal on repeat the participant will be excluded.
- Collect urine sample for urinalysis (see Section 14.1 for details)
- Record concomitant medications
- Administer C-SSRS (see Section 16.1 for details)

The following procedures will be performed as part of the Step 2/ Screening visit/s:

- Perform brain MRI
- Record any SAEs that have occurred since the Screening Visit

The following procedures will be performed as part of the Step 3/ Screening visit/s:

- Perform brain amyloid imaging of the brain (e.g., C-PiB Imaging). Amyloid imaging may not be required if there is biomarker evidence of Alzheimer's disease based on prior amyloid PET imaging or CSF A $\beta$
- Record any SAEs that have occurred since the Screening Visit

The following procedures will be performed as part of the Step 4/ Screening visit/s:

- Perform C-UCB-J Imaging
- Perform F-FDG Imaging
- Perform a lumbar puncture and collect CSF samples for PK and PD analyses
- After participant has met all inclusion requirements up through step 4 of screening, the pharmacy should obtain the participant randomization assignment for study subject; ideally no less than one week before participant returns for baseline visit.
- Record any SAEs that have occurred since the last visit.

## 10.2.2 Visit 2, Study Day 1 – Baseline

### Baseline Visit

(Week 0) The baseline visit may only be initiated following completion of all Screening assessments and required approvals. The Baseline visit procedures may be completed over multiple days and will typically require at least two (2) visits. All baseline procedures, including randomization must be completed within 60 days of initiation of Screening Visit procedures.

Following completion of all baseline procedures and confirmation that the baseline  $^{18}\text{F}$ -FDG PET has passed central quality control, participants who continue to meet all protocol inclusion criteria and no exclusion criteria, will be randomized and dispensed study medication. The following will be conducted as part of the baseline visit activities:

- Perform cognitive testing and functional assessments (see Section 16)
- Perform interval history
- Administer C-SSRS (see Section 16.1 for details)
- Perform physical examination (see Section 15.1.3 for details)
- Measure and record vital signs and weight (see Section 15.1.5 for details)
- Perform 12-lead ECG (see Section 15.1.6 for details)
- Draw blood and prepare sample for serum chemistry and hematology (see Section 14.1 for details)
- Collect urine sample for urinalysis (see Section 14.1 for details)
- Draw blood and prepare samples for PK
- Record concomitant medications
- Record any SAEs that have occurred since the Screening Visit
- Administer first dose of study drug
- Dispense double-blind study drug as required up to day 85+/- 7
- Schedule participant to return for Visit 3 in 2 weeks.

### **10.2.3 Visit 3, Study Day 15**

The following procedures will be conducted on Day 15 ( $\pm 2$  days):

- Administer C-SSRS (see Section 16.1 for details)
- Perform physical examination (see Section 15.1.3 for details)
- Measure and record vital signs and weight (see Section 15.1.5 for details)
- Draw blood and prepare sample for serum chemistry and hematology (see Section 14.1 for details)
- Collect urine sample for urinalysis (see Section 14.1 for details)
- Draw blood and prepare samples for PK
- Record concomitant medications
- Record AEs
- Administer study drug for that day
- Perform study drug accountability
- Schedule participant to return for Visit 4 in 2 weeks.

### **10.2.4 Blood Draw, Study Day 21**

The following procedure conducted on Day 21 ( $\pm 1$  days):

- Draw blood and prepare sample for serum chemistry and hematology (see Section 14.1 for details)

### **10.2.5 Visit 4, Study Day 29**

The following procedures will be conducted on Day 29 ( $\pm 2$  days):

- Administer C-SSRS (see Section 16.1 for details)
- Perform physical examination (see Section 15.1.3 for details)
- Measure and record vital signs and weight (see Section 15.1.5 for details)
- Perform 12-lead ECG (see Section 15.1.6 for details)
- Draw blood and prepare sample for serum chemistry and hematology (see Section 14.1 for details)

- Collect urine sample for urinalysis (see Section 14.1 for details)
- Draw blood and prepare samples for PK
- Record concomitant medications
- Record AEs
- Administer study drug for that day
- Perform study drug accountability
- Schedule participant to return for Visit 5 in 2 weeks.

### **10.2.6 Visit 5, Study Day 43**

The following procedures will be conducted on Day 43 ( $\pm 2$  days):

- Perform MMSE
- Perform cognitive testing and functional assessments (see Section 14)
- Administer C-SSRS (see Section 16.1 for details)
- Perform physical examination (see Section 15.1.3 for details)
- Measure and record vital signs and weight (see Section 15.1.5 for details)
- Draw blood and prepare sample for serum chemistry and hematology (see Section 14.1 for details)
- Collect urine sample for urinalysis (see Section 14.1 for details)
- Draw blood and prepare samples for PK
- Record concomitant medications
- Record AEs
- Administer study drug for that day
- Perform study drug accountability
- Schedule participant to return for Visit 6 in 3 weeks.

### **10.2.7 Visit 6, Study Day 64**

The following procedures will be conducted on Day 64 ( $\pm 2$  days):

- Administer C-SSRS (see Section 16.1 for details)
- Perform physical examination (see Section 15.1.3 for details)
- Measure and record vital signs and weight (see Section 15.1.5 for details)
- Draw blood and prepare sample for serum chemistry and hematology (see Section 14.1 for details)
- Collect urine sample for urinalysis (see Section 14.1 for details) Draw blood and prepare samples for PK
- Record concomitant medications
- Record AEs
- Administer study drug for that day
- Perform study drug accountability
- Schedule participant to return for Visit 7 in 3 weeks.

### **10.2.8 Visit 7, Study Day 85**

The following procedures will be conducted on Day 85 ( $\pm 7$  days):

- Perform MMSE
- Perform cognitive testing and functional assessments (see Section 16)
- Administer C-SSRS (see Section 16.1 for details)
- Perform brain MRI
- Perform  $^{11}\text{C}$ -UCB-J Imaging
- Perform physical examination (see Section 15.1.3 for details)
- Measure and record vital signs and weight (see Section 15.1.5 for details)
- Perform 12-lead ECG (see Section 15.1.6 for details)
- Draw blood and prepare sample for serum chemistry and hematology (see Section 14.1 for details)

- Collect urine sample for urinalysis (see Section 14.1 for details)
- Draw blood and prepare samples for PK
- Record concomitant medications
- Record AEs
- Administer study drug for that day
- Perform study drug accountability
- Dispense study drug for remainder of study
- Schedule participant to return for Visit 8 in 3 weeks

#### **10.2.9 Visit 8, Study Day 106 (±2 days):**

The following procedures will be conducted on Day 106:

- Administer C-SSRS (see Section 16.1 for details)
- Perform physical examination (see Section 15.1.3 for details)
- Measure and record vital signs and weight (see Section 15.1.5 for details)
- Perform 12-lead ECG (see Section 15.1.6 for details)
- Draw blood and prepare sample for serum chemistry and hematology (see Section 14.1 for details)
- Collect urine sample for urinalysis (see Section 14.1 for details)
- Draw blood and prepare samples for PK
- Record concomitant medications
- Record AEs
- Administer study drug for that day
- Perform study drug accountability
- Schedule participant to return for Visit 9 in 3 weeks.

**10.2.10 Visit 9, Study Day 127 ( $\pm 2$  days):**

The following procedures will be conducted on Day 127:

- Perform MMSE
- Perform cognitive testing and functional assessments (see Section 16)
- Administer C-SSRS (see Section 16.1 for details)
- Perform physical examination (see Section 15.1.3 for details)
- Measure and record vital signs and weight (see Section 15.1.5 for details)
- Draw blood and prepare sample for serum chemistry and hematology (see Section 14.1 for details)
- Collect urine sample for urinalysis (see Section 14.1 for details)
- Draw blood and prepare samples for PK
- Record concomitant medications
- Record AEs
- Perform study drug accountability
- Schedule participant to return for Visit 10 in 2 weeks.

**10.2.11 Visit 10, Study Day 148 ( $\pm 2$  days):**

The following procedures will be conducted on Day 148:

- Administer C-SSRS (see Section 16.1 for details)
- Perform physical examination (see Section 15.1.3 for details)
- Measure and record vital signs and weight (see Section 15.1.5 for details)
- Draw blood and prepare sample for serum chemistry, hematology and coagulation panel (see Section 14.1 for details)
- Collect urine sample for urinalysis (see Section 14.1 for details)
- Draw blood and prepare samples for PK
- Record concomitant medications
- Record AEs

- Administer study drug for that day
- Perform study drug accountability
- Schedule participant to return for Visit 11 in 3 weeks.

#### **10.2.12 Visit 11, Study Day 169 (For Primary Study only: End of Treatment / Early Discontinuation)**

For subjects participating in the Primary Study only **and not participating in the Extension Study**, this visit will serve as the end of treatment visit.

The following procedures will be conducted on Day 169: ( $\pm 7$  days):

- Perform MMSE
- Perform cognitive testing and functional assessments (see Section 16)
- Administer C-SSRS (see Section 16.1 for details)
- Perform physical examination (see Section 15.1.3 for details)
- Measure and record vital signs and weight (see Section 15.1.5 for details)
- Perform 12-lead ECG (see Section 15.1.6 for details)
- Draw blood and prepare sample for serum chemistry and hematology (see Section 14.1 for details) as well as for coagulation testing (prothrombin time [PT/INR]).
- Collect urine sample for urinalysis (see Section 14.1 for details)
- Draw blood and prepare samples for PK
- Perform  $^{11}\text{C}$ -UCB-J Imaging
- Perform  $^{18}\text{F}$ -FDG Imaging
- Perform MRI Imaging
- Perform a lumbar puncture and collect CSF samples for PK and PD analyses
- Record concomitant medications
- Record any SAEs that have occurred since the last visit
- Administer dose of study drug
- Perform study drug accountability

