**DURATION OF STUDY:**

Each participant and caregiver will participate in a screening period of up to -60 days, followed by the primary double-blind treatment period of 24 weeks (169 days +/-2), followed by an optional double-blind treatment period of an additional 24 weeks (337 days +/-2). A follow up visit will occur 2 weeks after completion of dosing. Including the Screening period of 60 days, the total duration of participant participation in the study is up to 36 weeks for those undergoing the first six months of treatment and the follow up visit only and up to 60 weeks for those undergoing both six month double blind treatment periods. If a delay occurs with subjects progressing from the primary study to the extension study, a maximum of 4 weeks will be permitted. It is anticipated that enrollment will occur over 15 months and all protocol activities will be completed after 21 months, with an additional 3 months for data analysis.

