### **Post-study Adverse Event**

A post-study AE is an AE occurring up to 30 days after the treatment period.

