### **Treatment-emergent Adverse Events**

Treatment-emergent adverse events (TEAEs) are all AEs occurring during the treatment period or a pretreatment AE that worsens in intensity during the treatment period.

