5.5. Data Derived by Calculation

The following data fields for inclusion in the data listings will be derived by calculation:

AEs Single Period:

- Treatment-emergent Indicator for adverse event, assigned as Treatment-Emergent if

$(\text{Onset Date} + \text{Onset Time}) \geq (\text{Date of First Dose} + \text{Time of First Dose})$

Non Treatment-Emergent if

$(\text{Onset Date} + \text{Onset Time}) < (\text{Date of First Dose} + \text{Time of First Dose})$

- Adverse event time since first dose (in days, to two decimal places), calculated as $(\text{Onset Date} + \text{Onset Time}) - (\text{Date of First Dose} + \text{Time of First Dose})$
- Adverse event time since dose in current treatment period (in days, to two decimal places), calculated as $(\text{Onset Date} + \text{Onset Time} - \text{Date of Dose in Current Treatment Period} - \text{Time of Dose in Current Treatment Period})$

AE Duration:

- Adverse event duration (in days, to two decimal places), calculated as $(\text{Resolution Date} + \text{Resolution Time} - \text{Onset Date} - \text{Onset Time})$

Safety Assessments Change from Baseline:

- Baseline for Vital Signs, ECG parameters, serum clinical laboratory parameters will be the most recent scheduled assessment prior to first dose

Clinical Laboratory Assessments:

- If a clinical laboratory result is above the upper limit of normal, then Out of Range flag will be set to “H”
- If a clinical laboratory result is below the lower limit of normal, then Out of Range flag will be set to “L”
- Clinical Laboratory parameters that are outside the reference range and assessed as clinically significant will be identified as “Abnormal CS”
- Clinical Laboratory parameters that are outside the reference range and not assessed as clinically significant will be identified as “Abnormal NCS”

Pharmacokinetics:

- Actual collection time post-dose (in hours, to two decimal places) for PK blood samples for each dose day calculated as $(\text{Collection Date} + \text{Collection Time} - \text{Date of Dose} - \text{Time of Dose})$

Pharmacodynamics:

- Actual collection time post-dose (in hours, to two decimal places) for PD CSF samples for each dose day calculated as $(\text{Collection Date} + \text{Collection Time} - \text{Date of Dose} - \text{Time of Dose})$

Efficacy Assessments Change from Baseline:

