8.2. Safety Data Presentation and Analysis

All clinical safety and tolerability data will be listed for each subject.

Safety data will be summarized using descriptive statistics. Where summaries include changes from baseline, the relevant baseline value will be determined as described in Section 5.5 above.

All treatment-emergent adverse events reported in this study will be listed using MedDRA terms, as coded per the Data Management Plan. The number of subjects reported with AEs and the number of AEs reported following administration of the IP will be summarised by treatment, grouped according to system organ class and preferred term, using descriptive statistics. The order for system organ class will be according to the Internationally Agreed Order, as per the guidance document MedDRA® *Data Retrieval and Presentation: Points to Consider*, specific to the MedDRA version used for this study. Summaries of AEs will also be presented by severity and by relationship to investigational product. In these summaries, subjects will be counted only once per MedDRA term, for the AE of highest severity or least favourable relationship. Summaries will also be presented of SAEs and of AEs leading to study withdrawal.

Clinical laboratory parameters for clinical chemistry, hematology, coagulation, urinalysis and thyroid tests will be listed and summarised by treatment group and study timepoint. Medical assessments of blood and urine parameters will be summarised by treatment group and study timepoint. A summary of changes from baseline will also be presented for serum clinical laboratory parameters. Individual subject profiles will be presented for any laboratory parameters with at least one post-dose value outside the laboratory's reference ranges and deemed clinically significant.

Vital signs will be listed and summarised by treatment and study timepoint. A summary of changes from pre-dose baseline will also be presented.

Body mass will be listed and summarised by treatment and study timepoint. In addition, a summary of changes from pre-dose baseline will be presented.

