11.8. Changes from the Analysis Planned in the Protocol

There are no changes from the planned analysis described in the protocol.

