14.3 Safety Data Summaries

14.3.1 Adverse Event Summaries

- Table 14.3.1.1 Overall Summary of Treatment-Emergent Adverse Events by Treatment
- Table 14.3.1.2 Summary of Treatment-Emergent Adverse Events by MedDRA Term and Treatment
- Table 14.3.1.3 Summary of Treatment-Emergent Adverse Events by Intensity (Severity) and Treatment
- Table 14.3.1.4 Summary of Treatment-Emergent Adverse Events by Relationship and Treatment
- Table 14.3.1.5 Summary of Treatment-Emergent Adverse Events of at least Moderate Intensity and Related to Study Treatment, by Treatment

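### The SAP's treatment-emergent AE window has no end and no Day 169 cut although the extension is optional, and the visit lists from V11 on conflict with the AE-recording rules

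*Protocol*

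**What the plan says.** **Endpoint.** Protocol 6.2.1 puts the incidence and severity of AEs first among the primary safety endpoints. Protocol 17.4 says AE incidence will be compared across dose groups, including placebo.

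**Protocol definition.** Section 15.2.1 defines TEAEs as "all AEs occurring during the treatment period or a pretreatment AE that worsens in intensity during the treatment period". The treatment period is the time on study drug. Later events have their own class: "A post-study AE is an AE occurring up to 30 days after the treatment period".

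**SAP definition and tables.** SAP 5.5 has the entry "Treatment-emergent Indicator for adverse event, assigned as Treatment-Emergent if", followed by a single test: onset date and time at or after first dose. Every earlier onset is non-emergent, and no upper limit is given. SAP 8.2 then states: "The number of subjects reported with AEs and the number of AEs reported following administration of the IP will be summarised by treatment". Appendix 2 plans one set of five tables, beginning with "Overall Summary of Treatment-Emergent Adverse Events by Treatment". SAP 11.8 says: "There are no changes from the planned analysis described in the protocol".

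**Length of treatment.** The synopsis describes an "optional double-blind treatment period of an additional 24 weeks" after the first 24 weeks, and allows up to 4 weeks' delay between the two periods.

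**AE recording.** In protocol 10.2, the lists for V3 to V10 ask for AEs of any kind. At V11 the line becomes "Record any SAEs that have occurred since the last visit", and the same line appears at V12E, V13, V14 and V15. The lists for Day 183 and Visit 16 do not mention AEs.

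**The concern.** The efficacy (SAP 9.3), imaging (SAP 10) and CSF (SAP 11.7) analyses each have separate 6-month and 12-month versions. The AE tables do not, although safety is the primary objective. A participant who extends has twice the planned dosing time in which to have a first event, yet counts the same in the denominator. If extension uptake differs by arm, crude incidence will differ even when the drug does nothing. The direction cannot be predicted, because uptake by arm is unknown.

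The flag itself contradicts the protocol in two ways. Events in post-treatment follow-up are TEAEs in the SAP but post-study AEs in the protocol. A pretreatment AE that worsens on drug is a TEAE in the protocol but not in the SAP.

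The visit-list wording leaves the capture of non-serious AEs after Day 148 uncertain. It matters most at the early-discontinuation visit (V11 or V15), because protocol 9.5.1 does not require early discontinuers to attend follow-up. The study-wide stopping rules in protocol 7.3.1 also count moderate and severe related AEs, so they too depend on non-serious capture.

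**Working it through.** The plan states no AE rate or extension uptake, so there is no figure of its own to reproduce. The text comparison comes first, then an illustration of size.

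**1. Visit lists against the recording rules.** Tables 1 and 2 mark AE recording at every visit below. Protocol 15.2.2 requires all AEs through the follow-up visit, SAP 8.1 requires continuous monitoring, and note 11 to the tables confines SAE-only collection to Screening.

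| Visit | Section | AE instruction in the list |
|---|---|---|
| V11, Day 169 | 10.2.12 | SAEs only |
| V12, Day 183 | 10.2.13 | none |
| V12E, Day 211 | 10.2.14 | SAEs only |
| V13, Day 253 | 10.2.15 | SAEs only |
| V14, Day 295 | 10.2.16 | SAEs only |
| V15, Day 337 | 10.2.17 | SAEs only |
| V16 | 10.2.18 | none |

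All seven lists conflict with the rules: five ask for SAEs only and two are silent.

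**2. Effect of unequal uptake on crude incidence.** Planned dosing is 168 days without the extension and 336 with it, a ratio of 2.0. Assumptions: constant hazard, equal in all arms; 7 per arm (protocol 17.2); no dropout; extension uptake independent of earlier AEs; 24-week incidence p24 between 0.2 and 0.7.

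- 48-week incidence: p48 = 1 - (1 - p24)².
- Arm incidence with k of 7 extending: (k × p48 + (7 - k) × p24) / 7.
- Difference between arms: (k1 - k2)/7 × p24 × (1 - p24).

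| p24 | p48 | 5/7 extend | 2/7 extend | Difference | Difference at 4/7 v 3/7 |
|---|---|---|---|---|---|
| 0.2 | 0.36 | 0.314 | 0.246 | 0.069 | 0.023 |
| 0.3 | 0.51 | 0.450 | 0.360 | 0.090 | 0.030 |
| 0.5 | 0.75 | 0.679 | 0.571 | 0.107 | 0.036 |
| 0.7 | 0.91 | 0.850 | 0.760 | 0.090 | 0.030 |

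Mean exposure at 5/7 is 24 × (1 + 5/7) = 41.1 weeks. At 2/7 it is 24 × (1 + 2/7) = 30.9 weeks, a ratio of 1.33. The arm with more uptake looks worse. Equal uptake gives a difference of 0. One participant is 1/7 = 14.3 points.

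**3. Effect of a literal reading of the V11 list.** V10 is Day 148 and V11 is Day 169, so 21 of 168 days (12.5%) would have no instruction to record non-serious AEs. The fall in 24-week incidence is p24 - [1 - (1 - p24)^(147/168)]: 0.023 at p24 = 0.2, 0.045 at 0.5 and 0.049 at 0.7. The wording is the same for every arm.

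**4. The two effects are alternatives.** If sites follow the 10.2 lists, non-serious events do not accrue in the extension. If they follow the tables, the exposure problem in step 2 applies.

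**The case against.** The strongest reply is that the practical damage is small.

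- *The data bound the window.* AE collection ends at the follow-up visit two weeks after dosing, with 30 more days for SAEs (protocol 15.2.2). This stands as a limit on the open end, but the SAP does not say so, and it does not equalise 24 and 48 weeks of dosing.
- *Few pretreatment AEs exist to worsen.* If note 11 is followed, Screening yields only procedure-related SAEs. This stands: the omission is a departure from the protocol that will probably affect few events.
- *The lists are loosely drafted.* The Day 21 list also lacks an AE line, the V9 list lacks the dosing line, and recording SAEs does not forbid recording AEs. Protocol 15.2.3 also tells participants to report AEs for 30 days after discharge or early withdrawal, and has unresolved AEs tracked weekly. These are real safeguards, so lost events are not shown. No rule says which text prevails, however, so the contradiction remains.
- *Readers can separate the periods themselves.* Exposure is summarised (SAP 7.1, Table 14.1.3), time since first dose is derived for each AE, and the analysis is descriptive. This makes the repair easy. It does not supply a pre-specified common window, and under SAP section 1 further analyses chosen after unblinding count as post hoc.
- *The 7-11 points rest on an assumed 5/7 against 2/7 split.* This is correct. They also rest on no dropout and on uptake unrelated to earlier AEs. The range is an illustration, not a bound.

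**Conclusion.** The point holds and should be fixed. The SAP's TEAE rule is wrong as written against protocol 15.2.1, while SAP 11.8 declares no change. The only planned AE tables mix participants with a two-fold difference in planned dosing. All seven visit lists from V11 on disagree with the recording rules.

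Under the stated assumptions the spurious difference is 7-11 points at 5/7 against 2/7 uptake, 2-4 points at 4/7 against 3/7, and nothing at equal uptake. Even the largest of these is less than one participant per arm, so this is a bias in a descriptive table for a primary endpoint, not something the trial could detect. A literal reading of the V11 list would lower 24-week incidence by a further-assumed 2-5 points, by the same rule in each arm. Whether any event is actually lost cannot be told from the documents.

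**What to change.** 1. **Protocol 10.2.12 to 10.2.18:** reconcile the lists with Tables 1 and 2 and section 15.2.2, so that all AEs are recorded from V11 to V16.
2. **SAP 5.5:** align the TEAE flag with protocol 15.2.1 by giving the window an end and including pretreatment AEs that worsen. Otherwise, state the difference in SAP 11.8.
3. **SAP 8.2 and Tables 14.3.1.1 to 14.3.1.5:** let the main TEAE tables cover one common window, from first dose to the Day 169 visit or earlier discontinuation. Show extension-period and post-treatment follow-up events separately, and add events per person-time for the full period. State which period holds onsets in the permitted gap of up to 4 weeks before the extension.

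The cost is a protocol clarification, one edited SAP definition and one extra set of AE tables. Onset dates and dosing dates are already collected, so no new data are needed. The cut should be fixed before unblinding.
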